**Table 20: Distributions of Observed Events Under Different Event Rates**

Number of Events	Rate With a Sample Size of 30							
	0.05	0.1	0.2	0.25	0.3	0.35	0.4	0.5
> 1 event	78.5%	95.8%	99.9%	> 99.9%	> 99.9%	> 99.9%	> 99.9%	> 99.9%
> 2 events	44.6%	81.6%	98.9%	99.8%	> 99.9%	> 99.9%	> 99.9%	> 99.9%
> 5 events	1.6%	17.5%	74.5%	90.2%	97.0%	99.2%	99.8%	> 99.9%
> 10 events	< 0.1%	< 0.1%	6.1%	19.7%	41.1%	64.2%	82.4%	97.9%
> 15 events	< 0.1%	< 0.1%	< 0.1%	0.3%	1.7%	6.5%	17.5%	57.2%

With 30 participants within each cohort, precisions of 95% Wald CI (1.96 times standard error) for true event rate given different numbers of observed events are shown in [Table 21](#).

**Table 21: Precisions of 95% Wald Confidence Intervals for Event Rate**

Type	Number of Events for a Sample Size of 30							
	4	6	7	9	10	12	13	15
Estimate	0.13	0.20	0.23	0.30	0.33	0.40	0.43	0.50
Precision	0.12	0.14	0.15	0.16	0.17	0.18	0.18	0.18

## 10.2. Populations for Analysis

The populations for analysis are provided in [Table 22](#), and the associated endpoints are provided in [Table 23](#).

**Table 22: Populations for Analysis**

Population	Description
FAS	The FAS includes all study participants who received at least 1 dose of either study treatment. The FAS will be used for the summary of demographics, baseline characteristics, participant disposition, and overall efficacy analyses. Participants will be analyzed according to the dose to which they have been assigned.
Safety-evaluable	The safety-evaluable population includes all participants who received at least 1 dose of either study treatment. All safety analyses will be conducted using the safety-evaluable population. Treatment groups for this population will be determined according to the actual dose the participant received regardless of assigned dose.
DLT-evaluable	The DLT-evaluable population includes participants enrolled into Part 1 who received at least 75% of the planned doses of INCB099280 and axitinib (ie, 32 doses of INCB099280 and axitinib) at the level assigned during the DLT observation period or have had a DLT during the 3-week DLT observation period. DLT-evaluable participants will be summarized independently.
PK-evaluable	The PK-evaluable population includes all participants who received at least 1 dose of either study treatment and have provided at least 1 postbaseline sample for PK analysis.
Pharmacodynamic-evaluable	The pharmacodynamic-evaluable population includes all participants who received at least 1 dose of either study treatment and have provided a baseline sample and at least 1 postbaseline plasma sample for pharmacodynamic analysis.
PK/pharmacodynamic-evaluable	The PK/pharmacodynamic-evaluable population includes all participants who are both PK-evaluable and pharmacodynamic-evaluable.

**Table 23: Primary and Secondary Endpoints and Analysis Populations**

Endpoint	Population	Hypothesis	Population-level Summary Metric
DLT	DLT-evaluable	NA	DLT incidence rate
Incidence of TEAEs	Safety-evaluable	NA	TEAE incidence rate
PK	PK-evaluable	NA	Concentration of INCB099280 in plasma; estimates of PK parameters for INCB099280
Objective response	FAS	NA	ORR
Disease control	FAS	NA	DCR
DOR	Subset of FAS	NA	Median DOR

### 10.3. Level of Significance

This is an exploratory study, and no formal statistical tests will be performed. Unless otherwise specified, all confidence intervals will be 95% without multiplicity adjustment.

### 10.4. Statistical Analyses

#### 10.4.1. Primary, Secondary, and Exploratory Efficacy Analyses

All efficacy analyses will be performed independently for each disease cohort and dose level. Analyses for Part 1 and Part 2 participants with the same tumor type and treated at the same dose level may be combined.

##### 10.4.1.1. Objective Response

Objective response rate is defined as the percentage of participants with best overall response of unconfirmed CR or PR, as determined by investigator assessment per RECIST v1.1 ([Eisenhauer et al 2009](#)). The ORR and its exact 95% CI will be calculated separately for each cohort and dose for Part 1 and Part 2.

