**Table 4: Objectives and Endpoints**

Objectives	Endpoints
Primary	
To evaluate the safety and tolerability of INCB099280 in combination with axitinib (Part 1).	
 
• Occurrence of DLTs.
 
• Incidence of TEAEs, including assessment of physical examinations, changes in vital signs and ECGs, and analysis of clinical laboratory samples.
 
• Incidence of TEAEs leading to a dosing modification (treatment interruption, dose reduction, and permanent discontinuation of either study drug).
 

To assess the antitumor activity of INCB099280 in combination with axitinib (Part 2).	Objective response, defined as the best overall response of CR or PR by investigator assessment per RECIST v1.1.
Secondary	
To evaluate the safety and tolerability of INCB099280 in combination with axitinib (Part 2).	
 
• Incidence of TEAEs, including assessment of physical examinations, changes in vital signs and ECGs, and analysis of clinical laboratory samples.
 
• Incidence of TEAEs leading to a dosing modification (treatment interruption, dose reduction, and permanent discontinuation of either study drug).
 

To assess the antitumor activity of INCB099280 in combination with axitinib.	
 
• Objective response (Part 1), defined as the best overall response of CR or PR by investigator assessment per RECIST v1.1.
 
• Disease control, defined as the best overall response of CR, PR, or SD by investigator assessment per RECIST v1.1.
 
• DOR, defined as the time from the first CR or PR until disease progression by investigator assessment per RECIST v1.1 or death from any cause, whichever occurs earlier.
 

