## 8.2. Efficacy Assessments

Objective assessment of disease status is required, using evaluations by RECIST v1.1 for solid tumors (Eisenhauer et al 2009). The investigator's assessment will be used to determine responses and will be recorded in the eCRF.

Efficacy baseline assessments will be performed at screening, and further efficacy assessments will be performed throughout the study at the intervals defined in the SoA (see Table 3). Cycle delays should not interrupt the 6-week (or 12-week when applicable) scan interval; thus, tumor assessments and cycles may become out of sync. A central imaging vendor will not be used in this study.

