#### 8.2.1.2. Assessment of Disease Response During Treatment

The first 2 disease assessments should be performed 6 and 12 weeks ( $\pm 7$  days) after the first dose of INCB099280 and axitinib and then Q12W ( $\pm 14$  days) thereafter (see Table 3). Imaging assessments may be performed more frequently if clinically indicated.

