**Imaging should follow calendar days and should not be delayed for delays in cycle starts.**

Disease progression should be confirmed at least 4 weeks but less than 8 weeks after the first scan indicating disease progression in clinically stable participants as per guidelines in Section 6.6.8. A PET scan may be incorporated into the disease assessment to confirm progression per RECIST guidance. Participants who have unconfirmed disease progression may

continue on treatment until progression is confirmed, provided that they have met the conditions detailed in Section 6.6.8.

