##### 10.4.1.2. Disease Control

Disease control rate is defined as the percentage of participants with best overall response of CR, PR, or SD, as determined by investigator assessment per RECIST v1.1. The DCR and its exact 95% CI will be summarized separately for each cohort and dose for Part 1 and Part 2.

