## **Amendment 1 (28 MAR 2024)**

### **Overall Rationale for the Amendment:**

The primary purpose of this amendment is to update the dose of INCB099280 being evaluated and to update the clinical study design, including the clinical indications being enrolled and the statistical design. Additional changes are summarized below.

1. **Section 1, Protocol Summary (Table 1: Primary and Secondary Objectives and Endpoints); Section 3, Objectives and Endpoints (Table 4: Objectives and Endpoints); Section 10.4.1.2, Disease Control**

**Description of change:** Removed the time requirement for SD.

**Rationale for change:** Clarification.

2. **Section 1, Protocol Summary (Table 2: Key Study Design Elements; Figure 1: Study Design Schema); Section 2.4.1, Rationale for Treatment with INCB099280 and Axitinib in Rare Gynecological Cancers; Section 4.1.2, Dose Expansion; Section 5.1, Inclusion Criteria**

**Description of change:** Clarified the rare indications to be included in the study.

**Rationale for change:** Clarification.

3. **Section 1, Protocol Summary (Table 2: Key Study Design Elements; Figure 1: Study Design Schema); Section 2.4.2, Rationale for Treatment with INCB099280 and Axitinib Following Disease Progression with Prior Immunotherapy; Section 4.1, Overall Design; Section 4.1.1, Dose Finding; Section 4.1.2, Dose Expansion; Section 5.1, Inclusion Criteria; Section 10.1, Sample Size Determination**

**Description of change:** Added 2 new indications/cohorts to the study.

**Rationale for change:** To include participants with recurrent endometrial cancer and cervical cancer post treatment with chemotherapy and immunotherapy.

4. **Section 1, Protocol Summary (Table 2: Key Study Design Elements); Section 5.2, Exclusion Criteria (Criterion 4)**

**Description of change:** Removed language prohibiting prior treatment with an immune modulator.

**Rationale for change:** Updated study design.

5. **Section 1, Protocol Summary (Table 2: Key Study Design Elements; Figure 1: Study Design Schema); Section 4.1.1, Dose Finding; Section 10.1, Sample Size Determination**

**Description of change:** Reduced the total number of participants to be enrolled in the study.

**Rationale for change:** Updated study design.

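### The Part 2 primary ORR counts unconfirmed responses, which Tables 1 and 4 do not say; a confirmed ORR should be reported beside it for every cohort

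*Protocol*

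**What the plan says.** Table 4, in Section 3, gives the Part 2 primary endpoint as "Objective response, defined as the best overall response of CR or PR by investigator assessment per RECIST v1.1". Table 1 has the same definition. Neither table says whether a response must be confirmed.

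Section 10.4.1.1 does say: ORR is "the percentage of participants with best overall response of unconfirmed CR or PR", by investigator assessment, with an exact 95% CI per cohort and dose. Section 10.4.1.3 starts DOR at the earliest CR or PR and ends it at progression or death. The median is reported only when there are more than 5 responses.

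On timing, Section 8.2.1.2 states: "The first 2 disease assessments should be performed 6 and 12 weeks" after the first dose (± 7 days). Scans then follow every 12 weeks (± 14 days). Sections 8.2.1.3 and 8.9.2 keep participants on imaging if they stop treatment for reasons other than progression. Section 10.3 calls the study exploratory, without formal tests. Section 2.4.1 cites a 25% response rate for PD-1 monotherapy in clear cell gynecological cancer and 40% for a PD-1 plus anti-VEGF combination in clear cell cancer.

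**The concern.** With no hypothesis test and no control arm, the Part 2 conclusion on activity rests on the ORR point estimate and its interval in each cohort. Under the current definition, one qualifying assessment at any visit makes a participant a responder, whatever the next scan shows. Someone reading only the objectives tables would not learn this.

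At stake is what the headline rate can support. The rationale invites comparison with 25% and 40%. A cohort whose sustained response rate is close to the monotherapy figure could appear to have moved toward the combination figure through responses seen on one scan only. The confidence interval does not cover this, because it describes sampling error. Enrolling more participants would not remove the shift either.

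**Working it through.** **Inputs.** Cohort size 30 (Section 10.1); half-widths in Table 21; scan schedule in Section 8.2.1.2; external rates of 25% and 40% (Section 2.4.1). The share *f* of first responses that are not confirmed is not in the protocol. I assume 10% to 30%.

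**1. Reproduce the plan's own precision.** Table 21 uses 1.96 × √(p(1 − p)/30). For 6 events, p = 0.20: 1.96 × √(0.16/30) = 0.143, printed as 0.14. The other entries (4, 7, 9, 10, 12, 13 and 15 events) give 0.122, 0.151, 0.164, 0.169, 0.175, 0.177 and 0.179. All match the table.

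**2. Direction.** Every confirmed responder is also an unconfirmed responder. In any data set, therefore, unconfirmed ORR ≥ confirmed ORR. This needs no assumption.

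**3. Size.** Unconfirmed ORR = confirmed ORR / (1 − f).

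| Confirmed ORR | f = 10% | f = 20% | f = 30% |
|---|---|---|---|
| 10% | 11.1% | 12.5% | 14.3% |
| 20% | 22.2% | 25.0% | 28.6% |
| 25% | 27.8% | 31.3% | 35.7% |

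At a confirmed rate of 20%, the expected count in 30 participants rises from 6 to 6.7, 7.5 or 8.6. The shift is 2.2 to 8.6 points, against a half-width of 14.3 points. At 25% the shift is 2.8 to 10.7 points, and the gap between the two cited rates is 40 − 25 = 15 points.

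**4. Can the planned scans confirm a response?** Take the shortest gaps that the visit windows allow, in days from first dose:

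- Week 6 to Week 12: (84 − 7) − (42 + 7) = 28 days.
- Week 12 to Week 24: (168 − 14) − (84 + 7) = 63 days.

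The next scheduled scan therefore always falls at least 4 weeks after the previous scheduled one, and no extra imaging is needed. A response first seen at Week 12 does have to wait until Week 24.

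**5. Effect on DOR reporting.** If a cohort has 6 unconfirmed responders and 1 is not confirmed, 5 remain. That no longer exceeds the threshold of 5 for reporting a median.

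**The case against.** The strongest reply is that the definition is a deliberate, visible choice in an exploratory study. Table 23 lists no hypothesis for any endpoint, so no alpha, power or success threshold depends on it, and the analysis correctly estimates what it defines. Tables 1 and 4 are silent on confirmation and do not contradict Section 10.4.1.1. The shift is smaller than the sampling error at 30 participants. A confirmed ORR is not neutral either, because a responder who starts new therapy, withdraws or dies before the next scan counts as unconfirmed. The SAP may also already add a confirmed rate. All of this stands. It makes the point one of reporting, and it makes confirmed ORR as the sole primary debatable. It does not remove the one-way direction, or the fact that the protocol itself fixes the primary definition and the objectives tables do not show it.

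The protocol does not support several stronger readings that a reader might infer:

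- **Local reading inflates ORR.** The protocol does state "A central imaging vendor will not be used in this study". Upward bias from local reading is plausible, but neither its direction nor its size can be shown from the document. The subset argument does not need it.
- **The futility look is undermined.** At a confirmed rate of 5%, the chance of at least 2 responders in 20 is 26%; with f of 10% to 30% it becomes 31% to 42%. But Section 10.5 makes the rule nonbinding, and a Week 12 look cannot wait for Week 24 confirmation.
- **DCR is inflated by very brief stable disease.** Amendment 1 records "Removed the time requirement for SD", and Section 10.4.1.2 sets no minimum. The first scheduled scan, at Week 6 ± 7 days, already implies about 5 weeks. Only an earlier unscheduled scan could give less.
- **Transient responders enter DOR as very short responses.** DOR ends at progression or death, not at loss of response, so this does not follow automatically.
- **Progression is held to a stricter standard than response.** The rule "Disease progression should be confirmed at least 4 weeks but less than 8 weeks after the first scan" serves decisions on treatment beyond first progression (Section 6.6.8). It is not a parallel endpoint standard.

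**Conclusion.** The point holds as a matter of definition and reporting. The Part 2 headline ORR cannot be below the confirmed ORR and may exceed it, and the endpoint tables do not disclose that it is unconfirmed. The direction is certain. The size is not in the protocol. Under an assumed unconfirmed share of 10% to 30%, a confirmed rate of 20% is reported as about 22% to 29%, and 25% as about 28% to 36%. That is a systematic shift of roughly 2 to 11 points over these two rates, on top of a 95% half-width of about 14 points at 6/30. If nearly all first responses are confirmed, the shift is negligible.

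The protocol does not say whether the cited 25% and 40% are confirmed rates. Printing both versions lets the reader compare like with like either way. No stated sample size, precision or error rate is wrong.

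**What to change.** - **Section 10.4.1.1:** for every cohort, report a confirmed ORR with its exact 95% CI beside the unconfirmed ORR, preferably as the headline figure. Define confirmed as CR or PR still present at an assessment at least 4 weeks later, with the next scheduled scan sufficing.
- **Tables 1 and 4:** state whether objective response is confirmed or unconfirmed.
- **Section 10.4.1.3:** give DOR for confirmed responders as well.
- **Section 10.5:** keep the nonbinding Week 12 futility count on unconfirmed responses, and say so.

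The cost is amended wording and some added table rows, with no added imaging. There are real downsides. The headline ORR will be the same or lower. Responses first seen at Week 12 can be confirmed on schedule only at Week 24. Responders who leave follow-up before their next scan will count as unconfirmed. Some cohorts may have too few confirmed responders for a median DOR.

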##### 10.4.1.2. Disease Control

Disease control rate is defined as the percentage of participants with best overall response of CR, PR, or SD, as determined by investigator assessment per RECIST v1.1. The DCR and its exact 95% CI will be summarized separately for each cohort and dose for Part 1 and Part 2.

##### 10.4.1.3. Duration of Response

Duration of response is defined as the time from the earliest date of CR or PR to the earliest date of disease progression, as determined by investigator assessment per RECIST v1.1, or death due to any cause if occurring sooner than progression. For participants who have not had disease progression and are still alive at the time of the analysis, DOR will be censored on the day of the last evaluable disease assessment. For participants who have withdrawn from the study or have started other anticancer treatment, DOR will be censored on the day of the last evaluable disease assessment documenting absence of PD before study withdrawal or the start of the new anticancer treatment. The total number of objective responders, number of participants who had disease progression or died, number of participants censored, and the Kaplan-Meier estimate of median DOR and its 95% CI using the Brookmeyer and Crowley's method ([Brookmeyer and](#)

Crowley 1982) will be provided separately for each cohort and dose for Part 1 and Part 2 (if the number of responses is  $> 5$ ).

#### 10.4.2. Safety Analyses

The clinical safety data (eg, vital signs, ECGs, routine laboratory tests, AEs) will be summarized using descriptive statistics (eg, mean, frequency) for the safety-evaluable population. Safety analyses will be provided for each dose for Part 1 and Part 2. An analysis of the combined doses will also be provided for Part 1 and Part 2.

The DLT incidence rate along with a 90% CI based on exact binomial distribution will be provided for each dose level using the DLT-evaluable population. The participants with DLTs and the type of DLT will be listed by dose level.

The tolerability of study drug will be assessed by summarizing the number of participants with a TEAE leading to dose interruptions, dose reductions, and treatment discontinuations for either study drug.

##### 10.4.2.1. Adverse Events

A TEAE is any AE either reported for the first time or worsening of a pre-existing event after the first dose of study treatment up to 90 days after the last dose of study treatment or until the start of new anticancer therapy, whichever occurs first. Analysis of AEs will be limited to TEAEs, but data listings will include all AEs regardless of their timing to study treatment administration. Adverse events will be coded by the MedDRA dictionary, and severity of AEs will be based on the NCI CTCAE v5.0 using Grades 1 through 5.

The subset of AEs considered by the investigator to have a relationship to study treatment will be considered to be treatment-related AEs. If the investigator does not specify the relationship of the AE to study treatment, the AE will be considered treatment related.

The number (%) of participants reporting any TEAEs, any SAEs, any Grade 3 or higher TEAEs, irAEs, any treatment-related TEAEs, any treatment-related serious TEAEs, any treatment-related Grade 3 or higher TEAEs, any fatal TEAEs, and any TEAEs leading to treatment

interruption/reduction/discontinuation will be tabulated by MedDRA system organ class and preferred term.

#### **10.4.2.2. Clinical Laboratory Tests**

Laboratory data will be classified into Grades 1 through 4 using CTCAE v5.0 when applicable. The following summaries will be produced for the laboratory data:

Descriptive statistics of the value and change from baseline at each assessment time.

For laboratory parameters that have CTCAE grading, shift tables showing change in CTCAE grade from baseline to the worst postbaseline grade.

For laboratory parameters that do not have defined CTCAE grades, shift tables showing change from baseline to the worst postbaseline value using the low/normal/high classifications based on laboratory reference ranges.

Categorical laboratory data will be tabulated by visit at baseline and postbaseline visits when necessary. Potential DILIs will be listed. The criteria for determining potential DILIs will be provided in the Statistical Analysis Plan.

#### **10.4.2.3. Vital Signs**

Descriptive statistics for the value at each assessment and change from baseline will be provided for vital signs (ie, BP, pulse, respiratory rate, and body temperature). Vital sign results will be reviewed for clinically notable abnormalities, and the abnormal values for participants exhibiting clinically notable vital sign abnormalities will be listed. Alert vital sign values are defined as an absolute value outside the defined range and an absolute percentage change of > 25% from baseline. The abnormal values for participants exhibiting alert vital sign abnormalities will be listed.

#### **10.4.2.4. Electrocardiograms**

Descriptive statistics for the value at each assessment and change from baseline will be provided for each ECG parameter. Baseline will be determined as the average of all nonmissing values from ECGs before the first administration of study treatment.

Electrocardiogram values outside of predefined ranges will be considered abnormal. Participants exhibiting ECG values outside the normal ranges will be listed. Participants with alert ECG values, defined as both the absolute value and the percentage change from baseline being outside normal ranges, will be identified and listed.

#### **10.4.3. Pharmacokinetic Analysis**

Descriptive summary statistics will be generated for plasma INCB099280 and axitinib concentration data by study part, dose levels, visit, and nominal time for the PK-evaluable population. For Part 2, the summaries will be additionally grouped by disease-specific cohorts.

For each participant with evaluable PK data, NCA PK parameters on Cycle 1 Day 1 (ie,  $C_{max}$ ,  $t_{max}$ ,  $AUC_{0-4h}$ ) and on Cycle 2 Day 1 (ie,  $C_{max,ss}$ ,  $t_{max,ss}$ ,  $AUC_{0-12h}$ ,  $C_{avg}$ ,  $C_{tau}$ ,  $t_{1/2}$ ,  $CL_{ss}/F$ , and  $V_z/F$ ) will be calculated from the observed plasma concentration-time profiles of INCB099280.

Descriptive summary statistics will be generated for the NCA PK parameters by study part, dose

[figure not shown]
levels, and visit. For dose-independent parameters only, such as  $CL_{ss}/F$ ,  $t_{1/2}$ , and  $V_z/F$ , additional summaries across dose levels will also be generated.

The INCB099280 PK concentration data obtained in this study may be combined with data from other studies in the clinical development program to develop or refine a population PK model. This model will be used to evaluate the effects of intrinsic and extrinsic covariates on the PK of INCB099280, whichever is applicable.

In addition, model-predicted post hoc exposures of INCB099280 may be used for exposure-response analyses on clinical efficacy (such as RECIST response) and/or safety endpoints as deemed appropriate. Planning and the results of population PK and exposure-response analyses will be reported separately.

For each participant with evaluable PK data, post hoc NCA PK parameters after first dose (ie,  $C_{max}$ ,  $t_{max}$ ,  $AUC_{0-24h}$ ,  $C_{24h}$ ) and at steady state (ie,  $C_{max,ss}$ ,  $t_{max,ss}$ ,  $AUC_{0-12h}$ ,  $C_{avg}$ ,  $C_{tau}$ ,  $t_{1/2}$ ,  $CL/F$ , and  $V_z/F$ ) may be calculated from the population PK model–predicted post hoc plasma concentration-time profiles of INCB099280.

Descriptive statistics will be performed for post hoc estimates of plasma INCB099280 population PK model parameters as well as the post hoc NCA PK parameters by dose levels and/or across dose levels (for dose-independent parameters only, such as  $CL/F$ ,  $t_{1/2}$ , and  $V_z/F$ ) for the PK-evaluable population.

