**Table 3: Schedule of Activities (Continued)**

Visit Day (Range)	Screening	Treatment				EOT (± 7 d)	Follow-Up			Notes
	Days −28 to −1	Cycles 1-2			Cycles 3+		Safety		Disease Status	
		Day 1	Day 8 (± 3 d)	Day 15 (± 3 d)	Day 1 (± 3 d)		EOT + 30 d (+ 7 d)	EOT + 90 d (+ 14 d)	Q12W (± 14 d) After EOT	
PK assessments										
PK plasma (INCB099280)		X*			X†					Section 8.4. *Predose and 1, 2, and 4 hours postdose. †Predose at Cycles 4 and 8 only.
PK plasma (axitinib)		X*			X†	X				Section 8.4. *Predose only. †Predose at Cycles 4 and 8 only.

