#### 2.4.3.3. Pharmacokinetics

Preliminary PK data from participants with advanced solid tumors in Study INCB 99280-112 demonstrate that steady-state PK is achieved by Cycle 1 Day 8 with up to [REDACTED]-fold accumulation in  $C_{max}$  but up to [REDACTED]-fold in  $AUC_{0-4h}$ . The interindividual variability in  $C_{max}$  and  $AUC_{0-4h}$  is high ([REDACTED]% GCV) for the largest dose groups of 300 mg BID ( $n = [REDACTED]$ ) and 400 mg BID ( $n = [REDACTED]$ ; PK-evaluable population as of [REDACTED]). Such a magnitude of interindividual variability is comparable with that observed in healthy participants ([REDACTED]% GCV). The PK exposures appeared to increase proportionally as the dose increased up to 800 mg BID. The geometric mean of the observed steady-state trough concentrations consistently exceeded [REDACTED] for BID dose levels of  $\geq 300$  mg. Based on the overall experience with INCB099280 to date, the sponsor considers 400 mg BID to be the appropriate dose that should be used to further evaluate the efficacy and safety of INCB099280 in participants with solid tumors. At this dose, more than half (ie, [REDACTED]% based on population PK simulations) of the participants are expected to have steady-state trough concentrations above the target [REDACTED].

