**Table 4: Objectives and Endpoints (Continued)**

Objectives	Endpoints
Secondary (continued)	
To characterize the PK profile of INCB099280 when administered in combination with axitinib.	
 
• INCB099280 and axitinib plasma concentrations.
 
• INCB099280 PK parameters by NCA methods such as <math>C_{max}</math>, <math>t_{max}</math>, <math>AUC_{0-4h}</math>, <math>C_{max,ss}</math>, <math>t_{max,ss}</math>, <math>AUC_{0-12h}</math>, <math>C_{avg}</math>, <math>C_{tau}</math>, <math>t_{1/2}</math>, <math>CL_{ss}/F</math>, and <math>V_z/F</math>.
 

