**Table 7: Study Treatment Information**

	Study Treatment 1	Study Treatment 1
Study treatment name	INCB099280	Axitinib
Mechanism of action	PD-L1 inhibitor	VEGFR-1, VEGFR-2, VEGFR-3 inhibitor
Dose formulation	Tablet	
Unit dose strengths/dose levels	■ mg, ■ mg/400 mg BID	1 mg, 3 mg, 5 mg/2 mg BID, 3 mg BID, or 5 mg BID
Route of administration	Oral	
Administration instructions	
Administered as tablets BID every day with a glass of water.
 
INCB099280 may be administered either on an ■ or with a ■.a
 
Note: A ■ (a meal that exceeds ■ calories with ■% calories from fat) is acceptable if consumed at least ■ hours before or after dose administration.
 
Participants must swallow the tablets whole without chewing before swallowing. Tablets must not be crushed, split, or dissolved.
 
INCB099280 and axitinib should be taken in the morning and evening, approximately 12 hours apart. If the administration of either the morning or evening a dose is delayed by more than 4 hours compared with the usual time taken, the dose should be skipped.
 
Participants must be informed that if they miss a dose or vomit after taking the tablets, an additional dose should not be taken. The next dose should be taken at the usual time.
	
Packaging and labeling	
INCB099280 will be provided in a bottle.
 
Each bottle will be labeled as required per country requirement.
	
Axitinib will be provided in a bottle or as a blister pack.
 
Axitinib will be a commercial supply.
 
When applicable, each bottle or blister pack will be labeled as required per country requirement.

Storage	
■-mg tablets: Must be refrigerated.
 
Store at ■
 
■-mg tablets: Store at ■
	Axitinib does not require any special storage conditions.
Status of treatment in participating countries	Investigational	Approved

a An example of a ■ meal in the United States typically contains 11-14 g of fat and a total caloric value of 400-500 kcal (eg, 8 oz of skim [1% fat] milk, 1 boiled egg, and 1 packet flavored instant oatmeal made with water).

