#### **8.4.1. Blood Sample Collection**

INCB099280 and axitinib PK samples will be obtained before the first dose on Cycle 1 Day 1, Cycle 2 Day 1, Cycle 4 Day 1, and Cycle 8 Day 1. Postdose PK samples will be obtained for INCB099280 on Cycle 1 Day 1 and Cycle 2 Day 1 at 1, 2, and 4 hours. An axitinib PK sample will be obtained at the EOT visit (see [Table 19](#)).

On days of PK sampling, study treatment will be administered in the clinic (see [Table 3](#)) and participants should not consume a [REDACTED] meal (a

[figure not shown]
meal that exceed [REDACTED] calories with [REDACTED]% calories from fat) within at least [REDACTED] hours before or after INCB099280 dose administration. A trough (predose) PK sample will be collected early in the study visit, followed by administration of the study treatment and subsequent timed blood samples. Study drug will be administered with water.

[figure not shown]
Predose is defined as within 3 hours before administration of study drug.

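### Terminal half-life and Vz/F for INCB099280 at Cycle 2 Day 1 are to come from observed profiles that stop at 4 h, which cannot support a reliable terminal slope

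*Protocol*

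**What the plan says.** - **Endpoint.** Tables 1 and 4 of the protocol give, as a secondary endpoint, "INCB099280 PK parameters by NCA methods such as" Cmax, AUC0-12h, t1/2, CLss/F and Vz/F, among others.
- **Analysis.** Section 10.4.3 assigns Cmax, tmax and AUC0-4h to Cycle 1 Day 1. It assigns Cmax,ss, tmax,ss, AUC0-12h, Cavg, Ctau, t1/2, CLss/F and Vz/F to Cycle 2 Day 1. All of these "will be calculated from the observed plasma concentration-time profiles of INCB099280".
- **Sampling.** Section 8.4.1: "Postdose PK samples will be obtained for INCB099280 on Cycle 1 Day 1 and Cycle 2 Day 1 at 1, 2, and 4 hours". The schedule of activities (Table 3) agrees: "Predose and 1, 2, and 4 hours postdose", and after that "Predose at Cycles 4 and 8 only".
- **Dosing interval.** Table 7: "INCB099280 and axitinib should be taken in the morning and evening, approximately 12 hours apart".
- **Steady state and trough.** Section 2.4.3.3 reports that "steady-state PK is achieved by Cycle 1 Day 8". Section 8.4.1 says "A trough (predose) PK sample will be collected early in the study visit" and allows predose to be drawn up to 3 h before the dose. Section 8.4 has the actual time of the preceding dose recorded.
- **Model-based route.** Section 10.4.3 separately lists much the same steady-state parameters, t1/2 and Vz/F included, as post hoc values from a population PK model. That paragraph is optional.

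**The concern.** A terminal half-life needs concentrations on the declining log-linear limb, and Vz/F needs the same slope. The protocol fixes both the sampling times and the data source (observed profiles), and for these two parameters they do not fit together. An analysis plan can add a calculation rule, but it cannot supply samples that are not drawn between 4 and 12 h.

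At stake is part of a named secondary endpoint. Section 4.1 says the PK assessments are meant to identify any effect of the combination on INCB099280, and Section 10.4.3 commits to summarising t1/2 and Vz/F by dose level and across dose levels. As written, the sponsor must either report values that mostly reflect absorption or depart from the protocol.

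**Working it through.** **Inputs.** From the protocol: samples at 0 (predose), 1, 2 and 4 h; interval τ = 12 h; steady state before Cycle 2. The protocol states no figure for half-life or absorption rate, so these are assumed: ka 0.5, 0.75, 1.0 and 1.5 per h; true t1/2 4, 8, 12 and 20 h.

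**Step 1: points after the peak.** The observed window covers 4/12 = 33% of the interval. Observed samples after the highest one: two if it is at 1 h, one if at 2 h, none if at 4 h. Two points fit a line exactly, so log-linearity cannot be checked even in the best case.

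**Step 2: model.** One compartment, oral, steady state, unit scale, ke = ln 2 / t1/2:

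C(t) = ka/(ka − ke) × [e^(−ke·t)/(1 − e^(−ke·τ)) − e^(−ka·t)/(1 − e^(−ka·τ))]

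**Step 3: half-life from the 2 h and 4 h samples**, = 2 ln 2 / ln(C2/C4). Example, true t1/2 4 h and ka 1.5: C2 = 0.8574, C4 = 0.6433, so 1.386/0.287 = 4.8 h.

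| ka (per h) | Estimate, truth 4 h | Estimate, truth 8 h |
|---|---|---|
| 0.5 | 170 h | not computable (C4 > C2) |
| 0.75 | 12 h | 44 h |
| 1.0 | 7.1 h | 17 h |
| 1.5 | 4.8 h | 10 h |

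The highest sample falls at 2 h or 4 h in all 16 combinations, so at most one observed point follows the peak. The result depends on ka. With faster absorption (ka 2.0) and true half-lives of 2, 4, 6 and 8 h, the peak sample is at 1 h and the two-point estimate is 2.1, 4.3, 6.5 and 8.7 h.

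**Step 4: Vz/F.** Vz/F = (CLss/F)/λz = (CLss/F) × t1/2 / ln 2, so it carries the half-life error in proportion.

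**Step 5: predose placed at 12 h as a rescue for t1/2**, = 8 ln 2 / ln(C4/C0). Example, truth 4 h and ka 0.5: C4 = 0.6669, C0 = 0.2148, so 5.545/1.133 = 4.9 h. Over the grid the error is 0% to +24%. If predose is drawn 3 h early (9 h after the previous dose) but placed at 12 h, the same case has C9 = 0.3506 and gives 5.545/0.643 = 8.6 h. Over the grid the error is then +61% to +124%. Placing the sample at its recorded 9 h gives 5 ln 2 / ln(C4/C9) = 3.466/0.643 = 5.4 h, with errors from about 0% to +40% over the grid.

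**Step 6: AUC0-12h.** In this grid 48% to 66% of the true AUC0-12h lies after 4 h. With predose used at 12 h, the linear trapezoid for truth 4 h and ka 1.0 (C0 0.1728, C1 0.7175, C2 0.8138, C4 0.6691) is 0.445 + 0.766 + 1.483 + 3.368 = 6.061. The true value is 1/ke = 5.771, so the error is +5.0%. The grid range is about -1% to +5%. With predose drawn 3 h early and C9 = 0.2905, the sum is 0.504 + 0.766 + 1.483 + 3.838 = 6.591, or +14%, the largest in the grid. Over a wider assumed range (t1/2 2 to 24 h, ka 0.3 to 2.0) with predose on time, the error is -2.5% to +14.5% by linear trapezoid and -6.5% to -0.5% by linear-up/log-down. Cavg = AUC/12 carries the same relative error; CLss/F = dose/AUC moves the opposite way.

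**The case against.** - **The full-interval parameters can be recovered.** A reader might infer that AUC0-12h, Cavg and CLss/F are also out of reach because 4 to 12 h is unsampled. The protocol does not support that. Steady state is reached well before Cycle 2, predose is called a trough, and Ctau is listed for Cycle 2 Day 1 although no 12 h sample exists. Using predose as the 12 h value is the natural reading, and a computing rule of this kind can sit in the analysis plan. This stands.
- **Cycle 1 against Cycle 2.** It is tempting to say that the plan recognises the limit at Cycle 1 (AUC0-4h only) and forgets it at Cycle 2. But the first-dose predose sample carries no trough information, while the Cycle 2 one does. The contrast fits the predose-as-12-h convention.
- **Half-life might be rescued the same way.** In the ideal model the 4-to-12 h slope is within about 25% of truth, so calling t1/2 impossible to recover would be too strong. This stands in part. That slope rests on two points, one of them substituted, cannot be checked for log-linearity, and is badly off if an early predose is treated as a 12 h value. It is also not an observed profile, which is the source Section 10.4.3 names.
- **Spurious interaction.** A reader might infer that the combination would falsely appear to alter INCB099280 exposure. No comparison of t1/2 or Vz/F with monotherapy is planned, summaries are descriptive, and Section 10.3 plans no formal tests. Cmax, AUC0-4h and trough come directly from the planned samples.
- **Partly provided for.** The endpoint tables list the parameters only as examples, and the population PK route covers both. But Section 10.4.3 lists the Cycle 2 parameters exhaustively and firmly, while the model route is optional.

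**Conclusion.** Wrong as written for t1/2 and Vz/F only. Section 10.4.3 commits to obtaining both from an observed profile with at most two points after the peak, and with one or none whenever the highest sample is at 2 or 4 h. AUC0-12h, Cavg and CLss/F are estimable with modest error and need only their assumption stated.

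The point-counting follows from the protocol alone. The error sizes depend on an assumed one-compartment model and assumed rate constants, and would be small for t1/2 if absorption were fast enough to put the observed peak at 1 h. Table 19, which gives PK times, is not visible in the copy reviewed, but Section 8.4.1 and Table 3 agree. The consequence is confined to a descriptive secondary endpoint.

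**What to change.** 1. Remove t1/2 and Vz/F from the observed-profile list in Section 10.4.3 and from the noncompartmental list in Tables 1 and 4.
2. Name the population PK post hoc estimates, already described in Section 10.4.3, as the source of these two parameters.
3. State that AUC0-12h, Cavg and CLss/F on Cycle 2 Day 1 use the steady-state predose concentration as the 12 h value, and how a predose sample drawn early is handled, given that actual times are recorded.

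**Cost.** Wording only, with no added samples or visits. The downside is that two descriptive parameters become model-based and depend on the population PK analysis, at present optional, being carried out.
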